9.3. Intensity of Adverse Event

The Investigator will use the adjectives MILD, MODERATE, or SEVERE to describe the maximum intensity of the AE. For purposes of consistency, these intensity grades are defined as follows:

- Mild: Does not interfere with subject's usual function
- Moderate: Interferes to some extent with subject's usual function
- Severe: Interferes significantly with subject's usual function

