The eye with the worse visual acuity will be the study eye. If visual acuity is equivalent in both eyes, the eye with the largest area of GA will be the study eye unless the patient (in consultation with the surgeon) expresses an alternative preference. The study eye will be confirmed by the vitreoretinal surgeon.

STATISTICAL METHODS: All the efficacy data (anatomical and functional visual outcomes), [REDACTED] and [REDACTED] data and safety data (including laboratory safety) collected will be amalgamated into a single database with datasets constructed according to these categories. Unless otherwise stated, data will be summarised in aggregate by dose and route of administration. Further detail will be described in the statistical analysis plan.

Analysis Set

Two analysis sets will be defined. The Safety Analysis Set (SAF) will include all subjects who have undergone surgery and received GT005. The SAF will be used for analysis of safety and laboratory data. The Full Analysis Set (FAS) will include all subjects in the SAF who have baseline and at least one post-baseline value of GA area size via FAF in the study eye. The FAS will be used for analysis of efficacy data.

Data Descriptions

Data will be summarised by the subject population (SS, FAS, and subsets as applicable), Cohort/dose group (Cohorts 1 to 7, dose group [REDACTED] vg, and overall subjects), eye (Treated [Study Eye]/Untreated [Fellow Eye] for ocular evaluations and tests), and assessment (Weeks 1 to 48, or early termination, where appropriate). The long-term follow-up data (Visits 9 to 13) will be reported separately.

Categorical variables will be summarised as the number and percentage of subjects, and frequencies of events (if appropriate). Continuous variables will be summarised as number of subjects, mean, median, standard deviation, minimum, and maximum statistics. Graphical displays appropriate to these types of data may be used to present any important findings.

Demographics and Baseline Characteristics

Medical history and measures at baseline including: demographics, medical/surgical history, concomitant medication, laboratory safety, urine pregnancy testing will be summarised descriptively by dose and route of administration. No formal comparisons of the Cohorts will be made. Assessments made at screening/baseline

and post-surgery will only be included in their respective safety and efficacy tables, together with any post-baseline assessments.

Efficacy Assessments

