Part 2 (Cohort 4; dose-expansion) will enrol up to 20 subjects in Cohort 4 with GT005 delivered via the transvitreal procedure to further characterise the safety, dose response and efficacy of GT005. On completion of dose escalation, dose levels determined to be safe and tolerable by the DSMB in Part 1 (Cohorts 1 to 3), may be assessed in Cohort 4. The exact number of subjects that will be enrolled in Cohort 4 will be determined by the Sponsor based on the emerging safety, pharmacodynamic and clinical outcomes data.

Part 3 (Cohort 5 to 6; dose-escalation and evaluation of two doses of GT005 delivered with the Orbit SDS; subretinal delivery via a suprachoroidal cannulation) will enrol three to five subjects at the mid dose (████ vg; Cohort 5) and three to five subjects at the high dose (████ vg; Cohort 6), to evaluate the safety of GT005 treatment when delivered via the Orbit SDS. Part 3 (Cohorts 5 to 6) is independent of, and may be conducted in parallel to, Part 2 (Cohort 4). Dose-escalation will be evaluated by the

DSMB and will be assessed based on the Week 5 safety data for the first three subjects dosed in Cohort 5.

Part 4 (Cohort 7; dose-expansion of GT005 delivered with the Orbit SDS; subretinal delivery via a suprachoroidal cannulation) will enrol up to 20 subjects in Cohort 7 to further characterise the safety, dose response, and efficacy of GT005 treatment when delivered via the Orbit SDS. On completion of dose-escalation, dose levels determined to be safe and tolerable by the DSMB in Part 1 (Cohorts 1 to 3) may be assessed in Cohort 7. The exact number of subjects that will be enrolled in Cohort 7 will be determined by the Sponsor based on the emerging safety, pharmacodynamic and clinical outcomes data.

Analyses of data from the Orbit SDS will be based on data accumulated from US sites.

The study treatment consists of an AAV2 expressing hCFI. The treatment is administered as a single subretinal injection into one eye – “the study eye”. Both eyes will be assessed at the screening visit. If both eyes meet the eligibility criteria the study eye will be the worse seeing eye or the eye with the largest GA size for eyes with equivalent visual acuity unless the subject (in consultation with the surgeon) expresses an alternative preference.

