If the screening period is extended past the original 8-week screening period (8–12 weeks), standard ophthalmic exam, haematology/biochemistry, and visual acuity (BCVA/LLVA) assessments should be repeated. In the event, that GT005 administration is deferred during the surgical procedure (e.g., due to an AE occurring during surgery) the screening period may be extended up to 16 weeks if agreed by the Sponsor Medical Monitor. Additionally, if the screening period is extended past 12 weeks (12–16 weeks), in case of GT005 deferral, standard ophthalmic exam, haematology/biochemistry, visual acuity (BCVA/LLVA), and FAFs will be repeated.

Visit 2 will occur at a surgical site. Pre-surgery assessments will include any local requirements of the surgical site. Pre-surgery assessments should be performed within 7 days prior to surgery. The following assessment are also required pre-surgery:

Timing	Procedure
Prior to Entering the Operating Room (within 7 days prior to surgery)	
• Review of Medical/Surgical History including bleeding history• Vital signs• AE/SAE monitoring• Pre-surgery ocular safety check to verify there are no new ocular AEs that would halt surgery• Microperimetry, if this was omitted at screening, should be performed if feasible• Concomitant medication review including use of anti-thrombotic drugs■ [REDACTED]■ [REDACTED]• Urine pregnancy test (for women of childbearing potential) if the one performed at screening is more than 14 days old• Blood draw for:■ [REDACTED]• Visual acuity check:
○ A visual acuity check using ETDRS or Snellen chart (near card is permissible) must be performed on the study eye if >4 weeks have lapsed since the last BCVA with ETDRS assessment. If Snellen result is >3 lines (BCVA equivalent to 15 letters) worse than the previous BCVA ETDRS score, then a BCVA with ETDRS assessment must be repeated. If the BCVA ETDRS score in the study eye is either >15 letters worse than the previous BCVA ETDRS score or <24 letters score (Cohorts 4 to 7), the surgery must be postponed

7.2. Visit 2 Day 2 (Post-Operative discharge); at a Surgical Site:

Subjects will be maintained in the clinic for up to 24 hours following the subretinal injection to assess any acute issues resulting from the surgery. The following post dosing assessments will be performed:

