11.3.4. Safety

The assessment of safety will be based primarily on the following: AEs, ophthalmic examination, BCVA/LLVA scores (ETDRS), vital signs, laboratory safety (biochemistry and haematology), and [REDACTED]

Adverse Events

Adverse events will be collected and recorded throughout the study and verbatim AE terms will be coded (to preferred terms) using terminology from MedDRA.

A TEAE is defined as an AE that is first identified, or is identified to worsen in intensity, on or after the subject receives the study medication during surgery.

The incidence, maximum intensity, and relationship to study medication or procedure of TEAEs will be summarised by system organ class and preferred term, according to dose and route of administration, as appropriate, and classified as systemic or ocular (Treated [Study Eye]/Untreated [Fellow Eye] or Both eyes).

All AEs, SAEs, AESIs, AEs leading to discontinuation, and deaths will be listed.

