### 3.9. Safety Analyses

#### 3.9.1. Adverse events

Analyses of adverse events will be performed in the SAF for treatment-emergent adverse events (TEAE). TEAEs are adverse events that are first identified or worsened after receiving the study treatment. Only treatment-emergent adverse events will be presented in the summary tables. Adverse events will be coded using the MedDRA dictionary and presented by system organ class (SOC) and preferred term (PT). The number (and proportion) of patients with TEAEs will be summarized by treatment dose and administration route at each analysis timepoint according to Table 5. AEs occurred after surgery for treatment administration and before deferred GT005 administration will be listed and included in footnotes of relevant TEAE summary tables.

**Table 5** TEAE summaries by treatment dose per administration route (if applicable)

TEAE summary	AE categories		
	Ocular AE in the study eye	Ocular AE in the fellow eye	Non-ocular AE
All AEs by primary SOC and PT	Y	Y	Y
All AEs by maximum severity	Y	Y	Y
AEs related to study treatment by SOC and PT	Y		Y
AEs related to surgical procedure by SOC and PT	Y		Y
AEs related to Orbit SDS procedure by SOC and PT	Y		Y
SAEs by SOC and PT	Y	Y	Y
SAEs related to study treatment by SOC and PT	Y		Y
SAEs related to surgical procedure by SOC and PT	Y		Y
SAEs related to Orbit SDS procedure by SOC and PT	Y		Y

All adverse events occurring in the study will be listed in subject data listings. By-subject listings will also be provided for the following: subject deaths; serious adverse events;

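### AE intensity is graded on the whole person while the treated eye is by default the worse-seeing one, so the ocular severity table can understate study-eye vision loss, and the readable SAP has no count of eyes with substantial loss

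*Protocol*

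**What the plan says.** **Grading scale.** Protocol Section 9.3 has three grades, all tied to the subject's usual function. The lowest is "Mild: Does not interfere with subject's usual function" and the highest is "Severe: Interferes significantly with subject's usual function". No readable text ties a grade to the affected eye or to letters lost.

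**Which eye is treated.** The Synopsis, under Reference Treatment, says "The eye with the worse visual acuity will be the study eye". Section 3.1 makes this conditional: "If both eyes meet the eligibility criteria the study eye will be the worse seeing eye or the eye with the largest GA size", with equal acuity as the trigger for the lesion-size rule and with room for the subject to prefer otherwise. Section 4.2 admits monocular subjects. Section 1.6.1.2.1 describes leaving the better eye untreated as a way to limit risk.

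**Where the grade is used.** SAP 3.9.1, Table 5, has a row "All AEs by maximum severity", with separate columns for ocular events in the study eye and in the fellow eye.

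**What counts as a TEAE.** Protocol 11.3.4: "A TEAE is defined as an AE that is first identified, or is identified to worsen in intensity", on or after dosing. SAP 3.9.1 accepts events first identified or worsened after treatment, and does not mention intensity.

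**Acuity.** SAP 3.9.2 summarises actual BCVA and LLVA and their change from baseline by visit, eye, dose and route, with mean-change plots and full listings. SAP 3.1 adds median, quartiles, minimum and maximum for continuous variables.

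**The concern.** The primary objective is safety, and the SAP plans no hypothesis tests, so the descriptive tables are the evidence. A grade based on the whole person's function is a weak measure of what happened to one eye when the other eye carries daily life. The subject can lose a good deal of acuity in the treated eye and carry on as before. The event is then mild as the scale is written, whereas the same loss in a better fellow eye could be moderate or severe. The fellow eye is the protocol's named comparator, so a reader will set the two severity columns side by side although they are not on a comparable footing.

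The same scale enters the protocol's TEAE definition. A condition already present at dosing, such as a cataract or reduced acuity, qualifies under that definition only if its intensity rises. If it worsens without changing usual function, the grade does not move.

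**Working it through.** The documents state no figure to reproduce here. The check is mostly one of rules, with a small calculation for scale.

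**1. Grade of a study-eye loss, by situation**

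| Situation | Effect on usual function | Grade the scale allows |
|---|---|---|
| Study eye is the worse eye, fellow eye intact (default) | Possibly none | Mild |
| Study eye is the better eye (subject preference, or only that eye eligible) | Likely some | Moderate or severe |
| Monocular subject | Direct | Moderate or severe |

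The understatement arises in the first row. The other two are the exceptions to the default.

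**2. TEAE status of the same loss**

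| Event | Protocol 11.3.4 | SAP 3.9.1 |
|---|---|---|
| Vision loss first identified after dosing | TEAE at any grade | TEAE at any grade |
| Condition present before dosing, worse after it, grade unchanged | Not a TEAE | Can be a TEAE, but no rule says how worsening is judged |

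SAP Section 4 declares no changes from the protocol-defined analyses, so the difference in the second row is unacknowledged. TEAE incidence over 48 weeks is the primary endpoint.

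**3. What the BCVA summaries can and cannot show**

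Take a dose and route group of 20 eyes (an assumed size; Cohorts 4 and 7 each enrol up to 20, possibly at more than one dose). The minimum change shows the single worst eye. The lower quartile lies between the fifth and sixth lowest values, since 20 × 0.25 = 5. One to four eyes losing more than 15 letters can therefore give the same minimum and lower quartile, a range of 1/20 = 5% to 4/20 = 20%. The listings contain the answer, but the reader must count it.

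SAP 3.1.1 also keeps unscheduled-visit data out of by-visit tabulations, and an acute loss may be measured at just such a visit. The same section admits those data to summaries over all post-baseline values, so an any-visit count would include them.

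**4. Illustration of size (assumed)**

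Suppose 3 of 20 study eyes lose more than 15 letters, all three are graded mild, and a loss of that size would otherwise have been graded above mild. Exact (Clopper-Pearson) 95% intervals for events above mild:

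- as tabulated: 0/20 = 0%. The upper limit is 1 − 0.025^(1/20) = 16.8%, so the interval is 0 to 16.8%;
- as an eye-level count: 3/20 = 15%, interval 3.2 to 37.9%.

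**The case against.** The strongest case against is that substantial vision loss is captured in several ways that do not use the grade. The SAE criteria in Section 9.1 include persistent disability and medically significant events, and SAP Table 5 tabulates SAEs by eye. A DSMB stopping criterion in Section 24.1 refers to reduced remaining vision. BCVA change is tabulated by eye with quartiles and minimum, and is listed. Protocol 11.3.4.1 and 11.3.4.2 also promise treated-minus-untreated differences for acuity. The AESI criteria are redacted and may contain a letter threshold. Worse-eye treatment is a default, not a fixed rule, and investigators may in practice grade ocular events by eye.

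Most of this stands, and it rules out two stronger readings. A reader might infer that study-eye vision loss could go unseen; the routes above show that the documents do not support that. A reader might also infer that it could drop out of the TEAE count; new loss cannot, at any grade, and the question touches only pre-existing conditions under the protocol's wording.

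The routes still leave a gap. Disability is itself judged on the person, and the readable text does not define medically significant. The DSMB criterion concerns stopping dose escalation for related toxicity within five weeks, whereas the primary period is 48 weeks. The expansion cohorts, up to 20 + 20 = 40 of about 65 subjects, are not escalation steps. The treated-minus-untreated differences do not appear in the readable SAP 3.9.2. None of these gives the number of eyes with substantial loss.

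A further fair objection is that the 15-letter threshold is a pre-surgery check (">15 letters worse than the previous BCVA ETDRS score" leads to postponement), not a definition of harm. It is used below as a reporting cut-off already familiar to the sites, not as a severity grade.

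**Conclusion.** The point holds in limited form. As written, Section 9.3 lets a substantial loss in a worse-seeing study eye be graded mild, and the study-eye column of the maximum-severity table can then understate harm relative to the fellow eye. The readable plan has no count of eyes with substantial loss to set beside it. Separately, the protocol and SAP definitions of a TEAE differ for conditions present before dosing and need reconciling.

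The documents do not show that the severity table is in fact biased, or by how much. That depends on how investigators graded and on which eye supported function, and neither can be estimated from the text. The 0/20 against 3/20 contrast assumes that every such loss was graded mild and would otherwise have ranked higher. The conclusion also assumes that usual function rests largely on the better eye, which is reasonable but not stated in the plan, and that the redacted AESI text does not already supply an equivalent count.

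**What to change.** 1. **SAP 3.9.2:** add the number and percent of study eyes and fellow eyes with a BCVA loss of more than 15 letters from baseline, by dose and route. Give it at each scheduled visit and at any post-baseline visit, with unscheduled visits included in the any-visit count. Present it alongside the maximum-severity table.
2. **Protocol 11.3.4 and SAP 3.9.1:** use one TEAE definition, and state how worsening of a pre-existing ocular condition is determined.
3. **Clinical study report:** note that Section 9.3 severity is person-level and does not measure the function of the affected eye. If 9.3 is amended so that ocular events are graded on the affected eye alone, identify earlier events as graded on the old scale, so that two scales are not mixed in one table without notice.

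The cost is one extra table from BCVA data already collected, plus some wording. The table covers past events without regrading. Reported ocular safety may look less favourable.

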9.4. Causality Assessment

When assigning relatedness of the AE, consideration will be given to whether there is a plausible relationship to either the study medication or the surgical procedure. For Cohorts 4 to 7, AEs deemed related to the surgical procedure will be considered to be related to either the transvitreal procedure or to the suprachoroidal cannulation procedure with the Orbit SDS, depending on the route of GT005 administration. AEs related to the suprachoroidal cannulation procedure with the Orbit SDS are considered device -related events.

AE severity and relationship to the study medication or the surgical procedure will be assessed at the site by the Investigator or a medically qualified designee.

The following are definitions of relatedness that will be used in this study:

Related: reports including good reasons and sufficient information (e.g., plausible time sequence, dose-response relationship, pharmacology, mechanics of surgical procedure) to assume a causal relationship to the study medication or the surgical procedure. In the sense that it is plausible, conceivable or likely.

Not related: reports including good reasons and sufficient information (e.g., implausible time sequence and/or attributable to concurrent disease or other drugs) to rule out a causal relationship to the study medication or the surgical procedure with GT005 administration.

Unknown: there is insufficient information to assess plausibility of causal relationship to the study medication or the surgical procedure.

9.5. Action Taken Regarding the Study Drug

The action taken regarding study drug must be described by selecting one of the following:

- Dose not changed – no action taken
- Drug withdrawn – not administered
- Dose reduced – partially administered
- Unknown/not applicable

9.6. Outcome

Each AE must be rated by selecting one of the following:

- Recovered/resolved
- Recovering/resolving
- Not recovered/not resolved
- Recovered with sequelae/resolved with sequelae
- Fatal
- Unknown

9.7. Recording Adverse Events

It is the responsibility of the Investigator to collect all AEs (both serious and non-serious).

All AEs occurring during the study must be documented on the appropriate section of the eCRF.

If an AE is considered serious, it must also be recorded on the Serious Adverse Event Form provided separately.

9.8. Reporting Serious Adverse Events and Adverse Events of Special Interest to the Sponsor

All AESIs and SAEs occurring from informed consent through to the long-term follow-up section of the study, or if the subject is not taking part in the long-term follow-up part of the study, until resolution of the event will be reported immediately (within 24 hours) by the Investigator, Contract Research Organisation (CRO) and/or Sponsor to the [REDACTED] Safety team, regardless of causal relationship. The applicable form (electronic data capture or back-up form) must be filled in by a member of the research team and kept in the Investigator site file.

All SAEs/AESIs must be reported in the eCRF. Alternatively, if the eCRF cannot be accessed, please contact [REDACTED] by telephone, fax or email:

[REDACTED] **SAE hotline – United States:**

Telephone: [REDACTED]

Fax: [REDACTED]

e-mail: [REDACTED]

OR

[REDACTED] **SAE hotline – Europe:**

Telephone: [REDACTED]

Fax: [REDACTED]

e-mail: [REDACTED]

Where the Investigator requires advice regarding the handling of SAEs/AESIs the contact in case of emergency is:

[REDACTED], ***dial 3 (United States)***

OR

[REDACTED] ***(Europe)***

A pregnancy is not considered to be an AE or SAE; however, it must be reported to Medpace Clinical Safety within 24 hours of knowledge of the event. Medpace Clinical Safety will then provide the Investigator/site the Exposure In Utero (EIU) form for completion. The Investigator/site must complete the EIU form and fax/email it back to Medpace Clinical Safety. The pregnancy should be followed until the outcome of the pregnancy, whenever possible. Once the outcome of the pregnancy is known, the follow-up EIU form should be completed and faxed/mailed to [REDACTED] Clinical Safety.

Gyroscope Therapeutics will report all relevant safety information about suspected unexpected serious adverse reactions (SUSARs) (and any new safety information that would adversely affect the safety of subjects or the conduct of the study) for the product under investigation to the Competent Authorities, Institutional Review Boards (IRBs)/Research Ethics Committee (RECs), Investigators and DSMB for the duration of the study as required by country-specific regulations.

In addition, any new safety information that would adversely affect the safety of subjects or the conduct of the study will be reported by Gyroscope to the Competent Authorities, Research Ethics Committees (RECs), DSMB and Investigators. If the study is to be suspended as a result of a SUSAR, or due to any urgent safety measure taken, Competent Authorities and RECs will be notified as soon as possible and within three days of the decision.

For study centres in the United States, Investigational New Drug safety reports will be submitted directly to the Investigators. It is the Investigators' responsibility to notify their IRBs/RECs in a timely manner. Gyroscope will submit Safety Reports to the applicable Competent Authorities and IRBs/RECs as required by country-specific regulations.

[REDACTED]

[REDACTED]

[REDACTED]

[REDACTED]

[REDACTED]

[REDACTED]

[REDACTED]

